2.1 Trial Summary

Fetal circadian rhythms are vital to normal fetal development and are dependent on maternal circadian rhythms until near-term. Preterm infants spend the first months of postnatal life in the disruptive setting of constant environmental light and noise, without maternal circadian inputs. Disturbed circadian rhythms are associated with *in utero* programming for late-onset metabolic syndrome, neonatal morbidity, and prolonged initial hospitalisation. Importantly, circadian rhythm disruption compromises neurodevelopment in animals. Cognitive impairment remains the primary morbidity associated with extremely preterm birth and increases health care costs. Therefore, we aim to establish if individual diurnal cycling of environmental light and noise levels improves cognitive outcomes of very preterm infants compared to more constant background lighting and noise.

We propose a multicentre, prospective, randomised, open, blinded end-point (PROBE) controlled trial that assesses the effect of non-invasive application of eye-masks and ear-plugs for 10 hours per night on neurodevelopmental, social, psychological, physiological, and economic outcomes. We hypothesise that diurnal cycling of light and noise commenced from birth and continued until discharge home will improve the cognitive score (Bayley-4), in infants born at < 32 w gestation. Primary outcome will be a mean difference of 4 points in the cognitive score on Bayley-4 at 2 years corrected postnatal age. Sample size to achieve 90 % power and alpha 0.05 is 954 infants, assuming a standard deviation of 15 points, a 10 % loss to follow-up and a 30 % adjustment for multiple births. Secondary outcomes will target anthropometry and growth, key neonatal morbidities (BPD/NEC/ROP/Sepsis/IVH), length of hospitalisation, survival, Bayley-4 sub-scores, infant behaviour, hormonal and clock gene circadian profiles, health service use, caregiver mental well-being and health economics.

3 Trial Rationale / Background

3.1 Background Summary

Prematurity (birth before 37 completed weeks gestation) is one of the most pressing health problems: globally, preterm birth accounts for more than 10 % of births and over 1.1 million neonatal deaths annually.¹ Cognitive impairment is the major and most distressing disability arising from preterm birth and the primary concern for parents and carers of preterm infants after hospital discharge. Cognitive impairment reflects the vulnerability of the preterm brain to disrupted development: children born preterm perform at >0.8 SD below term peers on IQ tests.² Premature babies also exhibit higher rates of adverse motor, behavioural and psychiatric outcomes in late childhood compared to children born at term gestation, even in the absence of recognised perinatal brain injury.³ Such life-long neurological deficits have enduring health and socio-economic consequences for these fragile infants, their family, and society. Rates of cognitive impairment after preterm birth have not improved in recent decades despite improved survival.^{4,5}

Circadian rhythmicity is essential to neurogenesis, learning, memory, and thus vital to development of normal cognition, as well as the structural and function integrity of developing organs.⁶

Circadian rhythmicity in circulating melatonin promotes onset of sleep at night when melatonin peaks, whereas peaking of the circulating cortisol levels in the early morning promotes wakefulness. The fetus is dependent on maternal circadian physiological cues (e.g. temperature; melatonin and cortisol) to orchestrate developmental processes until near term.^{7,8} Maternal circadian rhythm disruption (e.g. shift work), decreases fetal growth.⁹ Restricted fetal growth impedes short- and long-term fetal brain development and brain function (including intellectual, behavioural and motor functioning).^{10,11} In contrast, maternal melatonin improves neurodevelopment in the growth-restricted fetus.¹² Melatonin is neuroprotective for the developing brain: melatonin reduces inflammation, oxidative stress, lipid peroxidation, and cell death, and stabilises the blood-brain barrier after fetal asphyxia.¹³⁻¹⁶ Early endogenous production of this hormone thus has scientific credibility for improving neurodevelopmental outcomes. Rhythmic release of glucocorticoids are similarly vital for regulation of neural cell differentiation and death.¹⁷

Very preterm infants (<32 w gestation) have not yet developed a primary endogenous circadian rhythm,¹⁸ and are deprived abruptly of vital maternal circadian inputs after delivery. Furthermore, very preterm infants are cared for in neonatal intensive care units (NICUs) which have almost constant lighting and noise despite the efforts of staff. Bright light is a potent cue (zeitgeber) for regulation of circadian rhythms. Current

lighting guidelines suggest individual lighting of up to 2000 lux for specific procedures, where lux is a measure of light intensity.¹⁹ Similarly, cochlear damage or disrupted growth and development of premature infants may result from noise above 45 decibels. Further, preterm infants are exposed to neuroactive medications such as caffeine, or glucocorticoids, given at non-physiological times. Disrupted cues for circadian rhythmicity likely disrupts development of coordinated circadian rhythms critical for neurogenesis, organ growth and development.²⁰

Failure to deliver cyclical light/dark information to preterm babies delays development of autonomous circadian rhythms.²¹ Stress imposed from the constant light and noise of the environment may disrupt white matter organisation in the early postnatal months:¹⁰ white matter organisation at term is highly predictive for cognitive function at age 5 years,²² whilst rodent studies show that the severity of neurobehavioural disturbances are increased when circadian disruption is experienced during earlier rather than later period of brain development.¹⁰ Circadian rhythms reduce capacity for selective attention and executive function.²³ these complex cognitive tasks are frequently impaired in survivors of preterm birth.²⁴ Thus disrupted circadian rhythms may contribute to the increased incidence of subnormal academic achievement, attention-deficit/hyperactivity disorder and adolescent psychiatric disorders.²⁵ Impaired circadian rhythms may also increase vulnerability to autism spectrum disorder (ASD): birth before 34 weeks' gestation nearly doubles the risk of ASD compared to term infants;²⁶ further, the incidence and severity of ASD symptoms increase as gestation decreases.²⁷⁻²⁹ Exposure of preterm infants to constant light and noise also impedes growth trajectories and consequently prolongs initial hospitalisation. Such circadian disruption exerts key programming effects on the developing clock, increasing risk for later metabolic disease.^{30,31}

The American Academy of Pediatrics suggested introducing regular cycles of day-night lighting in the NICU in 1997,³² however there is no substantive clinical evidence to support this practice and few units achieve adequate (300 lux) separation of artificial night and day. To the contrary, the widely implemented Neonatal Individualised Developmental Care and Assessment Program (NIDCAP), recommences continuous dim lighting (< 20 lux) for 24 hours/day, to emulate the darkened environment of the uterus.³³ However, this continuous dim lighting eliminates any environmental zeitgeber input to the suprachiasmatic nucleus (which the fetus normally receives from circadian maternal cues). Even low levels of white light inhibit melatonin secretion, and in animal studies results in increased anxiety and delayed growth.³⁴ Importantly, preterm infants who are exposed to cycled light from birth develop circadian rhythmicity in melatonin profiles as early as five days of age:³⁵ this observation indicates they can respond to cycled light and is consistent with the timing of functionality in the retinohypothalamic pathway.³⁶

A 2016 Cochrane systematic review of cycled light versus a range of near darkness, or continuous bright light found likely benefit for cycled light for improved weight gain, oxygenation, and circadian activity patterns, and earlier hospital discharge.³⁷ Compared to continuous bright light, the weighted mean hospital stay for cycled light groups was significantly shorter (-16.5 d, CI -26.2 to -6.8). However, this 2016 review highlighted the poor quality of the seven randomised and quasi-randomised studies undertaken to date and inadequacy of sample size.³⁷ The Cochrane review findings of improved weight gain and earlier hospital discharge was reinforced by a 2017 trial evaluating the impact of cycled light commencing early (from 28 w PMA) or late (from 36 w PMA).³⁸ This most recent study is the only RCT to report the effect of cycled light on neurodevelopment: there were no neurodevelopmental differences observed between groups, however only 33 % (n = 40) of the cohort had neurodevelopmental assessments at 18 months postnatal age. The delay in starting cycled lighting until 28 w PMA meant some of extremely preterm infants spent up to 5 weeks without environmental cycling prior to commencing the intervention, despite no evidence of safety issues with light exposure on severity of retinopathy of prematurity (ROP)³⁹ or sensory development.⁴⁰ Further, night-time lighting protection only used cot-covers and dimmed ambient lighting, therefore preterm infants were exposed to light overnight for any medical procedures. Covering the eyes and protecting the babies from such inadvertent light exposure increases the duration of sleep per sleep epoch and total sleep per day.⁴¹

There are no studies of cycled noise exposure in preterm infants. The American Academy of Pediatrics recommends that NICU noise levels should not exceed 45 dB, but this is rarely achieved.^{42,43} However, one very small (n=24) centre study evaluated the use of silicone earplugs worn throughout the admission in very low birthweight (< 1500 g) infants. A mean (95 %) increase in weight at 34 w post-menstrual age of 225 (45, 405) g was noted in the group assigned to earplugs compared to controls. An even smaller (n=12) subset followed up at 18-22 months had an increased Bayley MDI of 15.5 (3.0, 28.0) and head circumference 2.6

(1.0, 4.2) cm. These outcomes need to be validated in an adequately powered trial with a primary neurodevelopmental outcome.

In summary, animal studies show early circadian rhythm development is vital for neurogenesis and works systemically to promote normal organ development and reduce risk of late-onset metabolic disease. Underpowered and low-quality studies in preterm infants suggest short-term benefits of early cycling of environmental light for improved weight gain, earlier hospital discharge and more stable physiology: each are determinants of cognitive capacity. Current developmental care guidelines promote continuous dim NICU lighting, but the Cochrane review suggests this approach is inferior to cycled light for short-term outcomes. The effect of cycled light on cognitive outcomes is unknown. Few studies have addressed the issue of noise in the NICU.

3.2 Intervention

Very preterm infants will be randomised to standard environmental care (control) or a cycled environment (light and noise) from birth until discharge. The intervention group will receive cycled environmental light and noise to simulate day/night-time environments using a pragmatic 14 hour day (6 am - 8 pm), 10 hour night (8 pm - 6 am) cycle.

- Daytime intervention will include exposure to light including removal of cot-covers if present, to achieve lighting within the range of 300-600 lux,⁴⁴ whilst avoiding direct bright light to the infant's eyes.
- Nocturnal intervention will include repositioning of cot-covers, application of light-occlusive eyemasks and silicone ear-plugs. Eye-masks and ear-plugs will remain in position during any medical procedures or overnight cares unless removal is necessary for medical reasons.

Similar cycling of cot-blankets in combination with cycled light was used previously in a small trial without adverse effects.⁴⁵ Light meters positioned within the infant's cot will be used to ensure daylight lux targets are achieved and maintained (intervention group) or level of ambient lighting recorded (control group).

Infants in the intervention group may still participate in the routine practice of afternoon 'quiet time' if required. This includes 1-2 hours of time in the afternoon where the lights in the nursery may be dimmed. Eye-masks, ear-plugs or cot covers should **not** be used for infants in the intervention group during 'quiet time' periods.

Eye-masks will continue to be used for phototherapy and ear-protection for high-frequency ventilation as per normal nursery protocols (normally short-term). Respiratory stimulants (e.g. caffeine) will be regulated to 8am dosing for all infants, when prescribed, to avoid pharmacologic confounding on circadian rhythm development. Similarly, if postnatal glucocorticoids are prescribed for severe lung disease, they will be given at 6 am/6 pm to reduce nocturnal disruption.

The proposed interventions (eye-masks, ear-protection) are already used in Australian NICUs as short-term protection from either phototherapy light, or noisy ventilators (e.g. high-frequency oscillators), and thus medically recognised as safe for neonates and acceptable to NICU staff. Additionally, we surveyed 17 parents of preterm babies enrolled in a circadian rhythm observational study regarding their attitudes to the research and proposed interventions. Parents ranked the mean (SD) importance of circadian rhythm research in newborn infants at 93 (9) on a scale of 0 (not important) to 100 (extremely important). 100 % of the parents studied indicated they would enrol their baby in a prospective study such as the CIRCA DIEM RCT. Parent satisfaction scores with our proposed physiological monitoring techniques were high: saliva and cheek swabbing procedures to obtain information on hormonal and clock gene rhythms mean (SD) score was 96 (7) whilst wearing of actimeters to monitor activity was 97 (6). Parents were largely accepting of adjustment of neuroactive medication timing (mean score 88 (16)), and similarly prepared to allow infants to wear eye-masks (77 (15)) and ear-plugs (77 (22)) overnight to block out light and noise. These survey responses indicate a high willingness of parents to engage with our proposed trial, and acceptance of proposed study intervention and monitoring.

4 Trial Aims / Objectives / Hypotheses

4.1 Objectives

The overall aim of the proposed study is to establish whether targeted individual diurnal cycling of environmental light and noise levels results in improved neurodevelopmental social, psychological, physiological, and economic outcomes of very preterm infants compared to more constant background lighting and noise environments.

4.2 **Primary Hypotheses and Outcome**

Exposure to cycled light and noise from birth until discharge home will increase cognitive score on the Bayley-4 at around 2 years cPNA.⁴⁶

4.3 Secondary Hypotheses and Outcomes

Exposure to cycled light and noise from birth until discharge home will: 1) improve neurodevelopmental sub-scores and neurobehaviour at 2 years cPNA; 2) not increase mortality or neonatal morbidities; 3) result in more rapid development of endogenous circadian rhythms; 4) reduce parental depression and anxiety and improve parent-infant interactions; and 5) decrease socio-economic costs of premature birth.

5 Trial Design

5.1 Study Endpoints

- 5.1.1 Primary outcome
 - Cognitive scores on the Bayley-4 around 2 years cPNA⁴⁶

The Bayley-4 is an individually administered instrument to assess developmental functioning in infants and young children from the age of 1 month to 42 months of age. The Bayley-4 is the current, universal national test of early development. The Bayley-4 sub-scores include cognitive, language (composite of receptive and expressive communication) and motor (composite of fine motor and gross motor). Scores are adjusted for prematurity, with a distribution centred on 100 with a standard deviation of 15. A 4-point change in cognitive score provides similar cognitive advantage as breast-feeding for at least 8 months and may be sufficient to obtain semi-skilled rather than unskilled work.⁴⁷ Expertise in Bayley-4 test administration is available within all Australian neonatal centres. A copy of the child's Bayley-4 results can be provided to parents upon request.

The trial will aim to conduct Bayley-4 assessments at 2 years cPNA. If participants are unable to undertake their Bayley-4 assessment at 2 years cPNA, a later Bayley-4 assessment will be undertaken as soon as reasonably possible and up to a maximum participant age of 3 years cPNA.

5.1.2 Secondary outcomes

Comprise short-term and longer-term neurodevelopmental and clinical outcomes as well as targeting physiological and molecular indicators of circadian rhythm development to inform mechanism and effectiveness of the intervention.

5.1.2.1 *Short term secondary outcomes*

- Survival to 36 w postmenstrual age (PMA)
- Weight, length, head circumference, and growth velocity (36 w PMA; 2 m, 6 m, 12 m cPNA)
 - Duration of hospitalisation
 - Tertiary hospital
 - Total duration of hospitalisation prior to first discharge home
- Severity of respiratory disease

•

- BPD (defined by the NICHD and shift of the oxyhaemoglobin dissociation curve),
- right shift of the SpO₂/P₁O₂ curve at 36 w PMA relative to the fetal oxyhaemoglobin dissociation curve
- duration of mechanical ventilation,
- duration any respiratory support
- days of oxygen supplementation
- Other neonatal morbidities including:
 - NEC stage II or more on Bell's classification
 - ROP stage II or stage III ROP, and presence of 'plus' disease or greater on ICROP3
 - Brain Grade 3 or 4 IVH, and presence of PVL
 - Sepsis defined as number of confirmed (blood culture positive) episodes of sepsis
- Risk for childhood neuromotor deficit using the Prechtl General Movements Assessment at 36 w PMA, 3 m and 3.5 m cPNA⁴⁸⁻⁵⁰
- Disability risk: 2, 6, 12 and 24 months (Ages & Stages Questionnaire-3 or the ASQ-TRAK)⁵¹
- Mother-infant attachment using the Maternal Postnatal Attachment Scale (19 items) score (36 w PMA; 2, 6, 12 months cPNA)⁵²
- Primary caregiver mental well-being (36 w PMA; 2, 6, 12 months cPNA).
 - Edinburgh Postnatal Depression Scale (EPDS)
 - Generalised Anxiety Disorder Scale (GAD-7).

5.1.2.2 Long-term (2 y cPNA) secondary outcomes

- Survival
- Proportion of scores < 1 SD and < 2 SD below mean, for the primary cognitive sub-score outcome at 2 y cPNA
- Individual components of the Bayley-4 at approximately 2 y cPNA
- Neurobehaviour using the Infant Toddler Social-Emotional Assessment (ITSEA)⁵³
- Social communication using the Communication and Symbolic Behaviour Scales Infant-Toddler Checklist (CSBS-ITC) for early recognition of risk behaviours that may be predictive of later behavioural difficulties such as diagnosis of autism spectrum disorder
- Growth velocity
- Anthropometry including weight, height, BMI, fat-free mass
- Primary caregiver mental well-being
 - GAD-7
 - Center for Epidemiologic Studies Depression Scale Revised (CESD-R).
- 5.1.3 Circadian rhythm biological sub-study (KEMH only, n=~70): confirming intervention effect on rhythms
 - Time to onset, mesor, amplitude, and acrophase of circadian rhythms in temperature, heart rate, oxygen saturation, salivary melatonin and cortisol and/or urinary melatonin, and buccal cell clock gene expression at study entry, 7 d, 14 d, 28 d and then 4 weekly until discharge home.
- 5.1.4 Social Communication sub-study (n=infants identified at risk of ASD using the CSBS-ITC, in centres where ADOS-2 testing is available)
 - Assessment at 2 years corrected postnatal age with The Toddler Module of the Autism Diagnostic Observation Schedule - Second Edition (ADOS-2)⁵⁴. Two outcomes will be reported from the ADOS-2.
 - the continuous scores of the ADOS-2 (i.e., autism behavioural severity)
 - the dichotomous outcome of whether or not children exceed the 'ASD' threshold (to be defined).
- 5.1.5 Neonatal lung function and body composition sub-study (KEMH only, n=128)
 - Tidal volume
 - Respiratory rate
 - Area under the flow volume curve
 - Body volume
 - Body fat and fat free mass, and % body fat

5.1.6 Measurement of infant sleep quality and duration sub-study

- Parents will be asked to complete the Brief Infant Sleep Questionnaire (BISQ-R; 33 items) at 2 months and 6 months corrected postnatal age, to provide detail on their infants sleep behaviours over the previous 2 weeks.
- Parents will also be asked to keep a sleep diary of their own sleep behaviours over the same interval.
- Infants and parents recruited to the sleep sub-study from KEMH or from Fiona Stanley Hospital (FSH), will also be invited to participate in physiological studies to measure how the cycled light and noise intervention influences sleep during hospitalisation (phase 1) and after discharge (phase 2).
 - Phase 1 (Completed December 2021): sleep and wakefulness will be measured using actigraphy at baseline, 7 d, 14 d, 28 d, and then every 4 weeks until 36 w postmenstrual age in infants recruited from KEMH.
 - Phase 2: sleep and wakefulness will be measured in both the infant and the main caregiver (parent) using actigraphy at 36 w postmenstrual age (or prior to discharge home, whichever comes first), at 2 months corrected postnatal age and at 6 months corrected postnatal age. Saliva swabs will also be obtained from the infants before they go to sleep at night, and again when they wake in the morning, at each of these times.

Key reported measures will include:

- Total sleep time
- Total day (6AM-8PM) and night (8PM-6AM) sleep
- Sleep/activity ratio
- Number of sleep awakenings after sleep onset
- Longest continuous sleep during daytime and night-time
- Peak salivary melatonin
- Day:night salivary melatonin ratio

5.1.7 Magnetic Resonance Imaging sub-study

MRI outcomes will include a calculation of a global abnormality score, derived from metrics obtained from T1- and T2-weighted images. Two different scoring systems will be applied to the conventional sequences.^{55,56}

Other MR measures of cerebral integrity will be derived from diffusion weighted imaging and include: Fractional anisotropy apparent diffusion coefficient in multiple areas of the brain.

An analysis of 208 MR images (n=104 from each group) will identify differences in the primary outcome of MRI Global Brain Abnormality Score (GBAS) of 2.85 assuming a standard deviation of 5 and adjusting for missing subjects (10 %) and 30 % multiple births.

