7.1.8 Assessment for autism (Social Communication sub-study, approved recruitment sites)

Infants with high CSBS-ITC scores will be eligible for a more formal evaluation of risk for ASD using the ADOS-2⁵⁴ at 2 y cPNA. The ADOS-2 will take approximately an hour to complete. The parent and child will be video recorded for scoring purposes. Once the videos have been scored, a single copy of the video will be retained on the Telethon Kids Institute server for the study data retention period with restricted access to the CIRCA DIEM study staff at the Telethon Kids Institute.

7.1.9 Measurement of infant lung function (neonatal lung function and body composition sub-study – KEMH only)

These measurements will tell us about the baby's normal breathing pattern and the size and function of the small airways. Tidal breathing, and respiratory mechanics will be obtained at 36 w PMA whilst the baby is in

quiet sleep. These measurements are minimally invasive and usually can be performed without disturbing the infant's sleep.

• We will record normal breathing volumes and respiratory rate, with a mask placed gently over the mouth and nose, while the baby is breathing spontaneously during quiet sleep using an ultrasonic flowmeter (Ecomedics Exhalyzer D).

7.1.10 Measurement of fat free mass (neonatal lung function and body composition sub-study)

- Infant fat-free mass is measured at 36 w cPNA using the PeaPod (Cosmed) non-invasive whole body densitometry device via air-displacement plethysmography technology for participants enrolled in the neonatal lung function and body composition study.
- Fat free mass will be obtained at 2 y cPNA using a compact & portable bioelectrical impedance monitor (Quantum III, RJL Systems) or similar.

7.1.11 Measurement of infant sleep quality and duration (infant sleep quality and duration sub-study) Sleep is assessed from 24 hour actimeter (ActiGraph GT9X Link) recordings at study entry, 7 d, 14 d, 28 d and 4 weekly until discharge home in infant participants. Study personnel will administer the actigraphy devices to the infant's ankle for measurement and will be responsible for device removal after a 24 hour recording period.

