10.1 Statistics and Interim Analysis

Data will be analysed in R software (open-source) on an intention to treat basis by the trial biostatistician ([name]) and performed blinded to study group assignment.

Missing data will be handled via multiple imputation.

Children unable to be tested on Bayley-4 due to death, disability, severe delay or performance below threshold for individual composite scores will be assigned a score of 49.

Comparability of study groups at baseline will be based on patient demographic data (birth weight Z-score, gestation, exposure to chorioamnionitis and maternal steroids, maternal shift work) and baseline physiological circadian rhythmicity determined at randomisation.

Descriptive statistics will include mean (SD), median (IQR) for continuous variables with symmetric and asymmetric distributions, respectively, and counts/percentages for categorical variables.

Cognitive scores between the two groups at 2 years cPNA (primary outcome) will be analysed using (1°) ttest and (2°) linear mixed effects regression, adjusted for socioeconomic status, parental risk index, sex, birthweight Z score, gestation age, antenatal and postnatal steroid use, key neonatal morbidity count and including random effects for multiple birth ID and site. The false discovery rate employed for all secondary analyses will use the Benjamini-Hochberg algorithm.

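### Both ADOS-2 outcomes are confined to children who screen positive on the CSBS-ITC, itself a post-randomisation outcome, so any comparison of arms within that group is open to selection bias

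*Protocol*

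**What the plan says.** Section 5.1.4 describes the sub-study population as "n=infants identified at risk of ASD using the CSBS-ITC", limited to centres where ADOS-2 testing is available. Section 7.1.8 repeats the gate: "Infants with high CSBS-ITC scores will be eligible for a more formal evaluation of risk for ASD".

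Two ADOS-2 outcomes are to be reported at 2 years corrected age: "the continuous scores of the ADOS-2 (i.e., autism behavioural severity") and "the dichotomous outcome of whether or not children exceed the 'ASD' threshold (to be defined"). Neither is given a denominator, and no ADOS-2 is planned in children who screen negative.

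Section 5.1.2.2 lists the screening instrument among the long-term secondary outcomes: "Social communication using the Communication and Symbolic Behaviour Scales Infant-Toddler Checklist (CSBS-ITC"). That entry carries no gate and no site restriction.

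Section 4.3 hypothesises that the intervention will "improve neurodevelopmental sub-scores and neurobehaviour at 2 years cPNA", and Section 3.1 gives as rationale that "Impaired circadian rhythms may also increase vulnerability to autism spectrum disorder (ASD"). Section 10.1 says that data will be analysed "on an intention to treat basis by the trial biostatistician", and Section 10.4 says that all recruited infants not withdrawn before discharge will be evaluated.

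**The concern.** The screen is applied after the whole intervention period and measures a domain that the protocol hopes to change. If the arms differ in who screens positive, the children who go on to ADOS-2 are no longer comparable by randomisation. A difference in ADOS-2 severity, or in the proportion over threshold, then mixes any effect on autism with the change in who was tested.

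Two wrong conclusions are possible. If the intervention mainly removes children without ASD from the screen-positive group, those left look more severely affected, and a harmless or helpful intervention can appear to raise autism rates. In the mirror case a real harm can be hidden. Either would be a consequential message about a device used in preterm infants.

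**Working it through.** **No figure to reproduce.** The protocol gives no sample size, power or event rate for this sub-study, and no ASD prevalence or CSBS-ITC accuracy. All rates below are assumptions chosen to show direction and range.

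**Binary outcome.** Let *p* be the ASD prevalence, *s* the screen's sensitivity and *f* the screen-positive rate among children without ASD. A child with ASD is taken to exceed the ADOS-2 threshold if tested.

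- Over threshold among those tested = *ps* / [*ps* + (1 − *p*)*f*]
- Screen-positive and over threshold among all followed infants = *ps*

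The control arm has *p* = 0.08, *s* = 0.90, *f* = 0.20 throughout: 0.072 / (0.072 + 0.184) = 28.1% of those tested, 7.2% of all. Sensitivity is 0.90 in both arms.

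| Intervention arm | Calculation among tested | Tested: control v intervention | All followed: control v intervention |
|---|---|---|---|
| ASD unchanged at 8%, *f* = 0.10 | 0.072 / (0.072 + 0.092) | 28.1% v 43.9%, spurious harm | 7.2% v 7.2% |
| ASD falls to 6%, *f* = 0.20 | 0.054 / (0.054 + 0.188) | 28.1% v 22.3%, right direction | 7.2% v 5.4% |
| ASD falls to 6%, *f* = 0.12 | 0.054 / (0.054 + 0.1128) | 28.1% v 32.4%, reversed | 7.2% v 5.4% |
| ASD rises to 10%, *f* = 0.32 | 0.090 / (0.090 + 0.288) | 28.1% v 23.8%, reversed | 7.2% v 9.0% |

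**When a benefit reverses.** The proportion among those tested rises when non-ASD screen-positives fall proportionally more than ASD screen-positives. With ASD falling from 8% to 6%, ASD positives fall by a quarter (7.2% to 5.4%). The break-even is therefore a fall by a quarter in non-ASD positives, from 18.4% to 13.8% of infants: *f* = 0.138 / 0.94 = 14.7%. Below that the sign is wrong; above it the sign is right.

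**Continuous score.** This was simulated with 1,000,000 children per arm. Severity is standard normal, the screen correlates 0.71 with it, and 25% of controls screen positive. Differences are intervention minus control, and a negative value means less severe.

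| True effect on severity | Extra shift on the screen | Difference among screen-positives |
|---|---|---|
| −0.30 SD | none | −0.19 SD, attenuated |
| 0 | −0.3 SD | +0.17 SD, spurious |
| −0.10 SD | −0.4 SD | +0.16 SD, reversed |

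**Limit of the wider denominator.** In the second simulated scenario, true ASD (severity above a fixed cut) is 8.1% in both arms, but the screened-and-confirmed proportion among all children is 6.5% v 5.4%. The shift on the screen lowers its sensitivity in the intervention arm, so read as ASD prevalence the composite suggests a benefit that is not there.

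**The case against.** The strongest reply is that the protocol never prescribes the faulty comparison. Section 5.1.4 says only that two outcomes will be reported; it names no test, estimand or denominator. Other sub-studies are more explicit: Section 5.1.7 gives a number per group and a difference to detect. Stating who is tested is not stating who is analysed. Intention to treat and Section 10.4 are compatible with a wider denominator for the binary outcome, which a SAP could supply. The CSBS-ITC already provides an ungated comparison, and only a sub-study is involved.

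Much of this stands. A reader might infer that the protocol commits to a between-arm test among screen-positives. The text does not say so, although listing the outcomes under Study Endpoints of a two-arm trial, and Section 10.2's generic sub-study target of a mean difference, make a comparison by arm the natural expectation.

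The reply does not dispose of the continuous score. Screen-negative children will have no ADOS-2 result, so no SAP can give severity an unselected comparison without strong assumptions. That follows from who is tested, which the protocol fixes.

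A reader might also infer that unblinded parents distort the screen. Section 5.3 does say families cannot be blinded, but it also says outcome assessors are, and the protocol does not state who completes the CSBS-ITC. The point does not need that argument.

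**Conclusion.** The point holds as a risk of selection bias in any between-arm ADOS-2 comparison made in the stated sub-study population. On the assumed rates, an intervention with no effect on ASD could show 28% v 44% over threshold among those tested. On the continuous scale, a null effect could appear as +0.17 SD.

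It is tempting to say that the result will be reversed. The documents do not support that: they give no screening rates, and reversal depends on the intervention changing screen positivity proportionally more in children without ASD than in those with it. If non-ASD positivity is unchanged, a true benefit keeps its direction (28.1% v 22.3%). If the intervention moves the screen only through severity, the effect is attenuated with the same sign. The 28% v 44% case is a spurious difference, not a reversal, because no true effect was assumed.

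Restriction to ADOS-2 centres is not in itself a bias, since randomisation is stratified by site. The primary outcome is unaffected. The section merits amendment, and its ASD threshold is still undefined in any case.

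**What to change.** Amend Section 5.1.4, and Section 7.1.8 to match:

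1. Name the CSBS-ITC in all followed infants as the main randomised comparison of social communication.
2. Define the binary ADOS-2 outcome as the composite of screen-positive and over the ADOS-2 threshold, among all randomised infants at ADOS-2 sites with a completed CSBS-ITC. Count screen-negative children as not meeting it.
3. Interpret the composite as screen-detected, ADOS-2-confirmed risk, not as true ASD prevalence. State that a difference between arms in screen sensitivity could still bias inference about ASD in either direction.
4. Report continuous ADOS-2 severity in screen-positive children as descriptive only, with no between-arm causal claim.

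This is a change of wording and needs no new assessments. Its price is that children with ASD missed by the screen count as negative, and that severity loses any claim to a treatment effect. Removing the remaining bias would need ADOS-2 in all infants at equipped centres, or in a random sample of screen-negatives with weighting, at the cost of further assessments of about an hour each (Section 7.1.8).
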